## 4.0 Study Endpoints

### Specific Aim 1:

#### **Primary pilot efficacy outcome variables include:**

Completion of SBIRT: We will compare the proportion of participants that complete a screen for mental health and substance use, the proportion of those screening positive that are referred to treatment, and the proportion of those referred to treatment that had at least one mental health and/or substance use disorder treatment appointment among those assigned to LTW, compared to TAU.

Time to Treatment: We will measure the time from completion of screening positive to time of first mental health or substance use treatment appointment (if a referral to treatment was appropriate) among those assigned to LTW, compared to TAU.

Reduction in Mental Health Symptoms: Among women referred for treatment, we will compare the mean change in the Edinburgh Postnatal Depression Scale (EPDS) among those assigned to LTW, compared to TAU. *Of note, the suicidal ideation question (item #10) will be omitted from this questionnaire.*

Reduction in Substance Use: Among women referred for treatment, we will compare change in substance use frequency and amount as measured by the NIDA-Modified Assist (see LTW protocol) among those assigned to LTW, compared to TAU.

Improved Maternal Functioning: Among women referred for treatment, we will compare the change in maternal functioning measured by the Medical Outcomes Study Short Form 36 (SF-36v2) among those assigned to LTW, compared to TAU.

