## 1.0 Objectives / Specific Aims

### Specific Aim 1

The goal of Specific Aim 1 is to develop an effective remote mental health and substance use Screening, Brief Intervention and Referral to Treatment (SBIRT) program for pregnant and postpartum women. The **objectives** of this current application for Specific Aim 1 are to conduct a pilot RCT of a text-message based SBIRT and home-based telemedicine services for pregnant and postpartum women – called Listening to Women (LTW), compared to treatment as usual (TAU) with the primary objective to provide effect size estimates for a larger RCT.

**Specific Aim 1:** Conduct a pilot, small-scale randomized controlled trial to examine feasibility and preliminary efficacy of LTW, compared to TAU. Outcomes related to feasibility include percentage of eligible patients recruited, **study attrition**, **study retention**, and mental health and substance use treatment appointment attendance. Outcomes related to **preliminary efficacy** will include participation in screening, referral and treatment at baseline, compared to TAU.

The central hypotheses for Specific Aim 1 are that the study is feasible and women assigned to LTW will be more likely to screen positive and successfully obtain treatment in less time, compared to those that are assigned to TAU.

### Specific Aim 2

Upon completion of Specific Aim 1, the goal of Specific Aim 2 is to evaluate the effectiveness of a remote mental health and substance use Screening, Brief Intervention and Referral to Treatment (SBIRT) program for pregnant and postpartum women. The **objectives** of this current application for Specific Aim 2 are to conduct an RCT of a text-message based SBIRT and home-based telemedicine services for pregnant and postpartum women – called Listening to Women (LTW), compared to treatment as usual (TAU) with the primary objective to include attendance to treatment at baseline, compared to TAU.

**Specific Aim 2:** Conduct a randomized controlled trial to examine the effectiveness of LTW, compared to TAU. Outcomes related to **effectiveness** include attendance to treatment at baseline, compared to TAU.

The central hypotheses are that a greater proportion of women assigned to LTW will attend treatment following a referral, compared to TAU.

### Specific Aim 3

The goal of Specific Aim 3 is to gather data related to maternal and newborn diagnosis codes, health care utilization, and costs for our study participants with Medicaid.

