**Secondary pilot feasibility and acceptability outcome variables include:**

Recruitment: We will determine the proportion of patients who agree to participate as compared to the total number solicited to enroll for each recruitment approach.

Attrition: We will examine the proportion of study participants that prematurely terminate i.e., do not complete screenings, or are unable to be contacted for referral and/or treatment.

Study retention: We will determine the proportion of study participants that complete all assessment points associated with the protocol.

Treatment Attendance: We will collect data from the EHR to determine the proportion of participants that attended a mental health or substance use treatment appointment.

Improved Health-Related Social Needs: Among women referred for treatment, we will compare the change in health-related social needs measured by the Accountable Health Communities (AHC) Health-Related Social Needs (HRSN) Screening Tool among those assigned to LTW, compared to TAU.

Voice Biomarkers: Voice analysis will be completed using an online platform SurveyLex (owned by NeuroLex, Inc.). Among women referred for treatment, we will analyze voice recordings for characteristics (acoustic, linguistic, or meta feature) which may be compared between those assigned to LTW and those assigned to TAU, and compared to other measures collected in either LTW or TAU including EPDS, NIDA Modified Assist, and/or AHC HRSN.

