Statistical Analysis Plan

Sample Size and Power Analysis

Using a chi-square testing framework and a significance level of 0.05 and assuming two-sided hypothesis testing, both primary and secondary outcomes included a large enough sample size to detect differences between groups. Our a priori group sample sizes (usual care: n=191; LTWP: n=224) provided 80% power to detect between-group absolute differences in proportions ranging from 6% to 12% in the primary study outcomes (for example, screened: 65.2% [usual care] versus 77.7% [LTWP]; screened positive: 21.7% versus 34.2%, respectively; referred: 12.5% versus 23.1%, respectively; and attended treatment: 2.1% versus 8.3%, respectively). Our group sample sizes among participants completing a screen (usual care: n=63; LTWP: n=221) provided 80% power to detect between-group absolute differences in proportions ranging from 11% to 18% in the secondary study outcomes (for example, screened positive: 17.5% [usual care] versus 35.4% [LTWP]; referred: 3.2% versus 15.3%, respectively; and attended treatment: 1.6% versus 12.3%, respectively). The usual care rates used in these calculations were based on data published from earlier work on the LTWP program.

Data Analysis

We will assess the adequacy of randomization by comparing LTWP versus usual care (UC) on demographic, obstetric, and psychiatric baseline characteristics, using t-tests or Wilcoxon rank sum tests for continuous variables and chi-square tests or Fisher's exact tests for categorical variables, respectively. Descriptive statistics will be calculated for each screening method (LTWP versus usual care), including counts and percentages for participants who were screened, screened positive, referred to treatment, and attended treatment. Unadjusted differences in outcomes between people assigned to LTWP versus UC will be calculated using chi-square tests because all study outcomes are dichotomous. Relative risk (RR) ratios will be estimated and reported along with their 95% confidence intervals. All hypothesis tests will be two-sided with a type 1 error set at 0.05, and all analyses will be performed using SAS statistical software, version 9.4 (Cary, NC).

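### Referral and attendance have inconsistent denominators across protocol and SAP; the nested and screened-only versions are not randomised comparisons, and the SAP's 80% power does not extend to the nested one

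*Protocol*

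**What the plan says.** The documents give referral and attendance several denominators.

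- **Nested (Protocol 4.0, Specific Aim 1, Completion of SBIRT).** The primary pilot efficacy outcomes include "the proportion of those screening positive that are referred to treatment, and the proportion of those referred to treatment that had at least one" treatment appointment, compared between LTW and TAU.
- **All participants (Protocol 4.0, Aim 1 feasibility outcomes, Treatment Attendance).** This is "the proportion of participants that attended a mental health or substance use treatment appointment". It is listed separately, and no between-arm comparison is stated.
- **Whole group (SAP, Sample Size and Power Analysis, primary outcomes).** "Our a priori group sample sizes (usual care: n=191; LTWP: n=224) provided 80% power" for screened, screened positive, referred and attended, with examples such as "screened positive: 21.7% versus 34.2%, respectively".
- **Screen completers (same SAP section, secondary outcomes).** Screened positive, referred and attended are powered again on 63 usual-care and 221 LTWP women.
- **Not stated (Protocol 4.0, Specific Aim 2, Primary Outcome).** Attendance means at least one visit during pregnancy or the postpartum year, with no denominator. The Aim 2 hypothesis in Protocol 1.0 is that "a greater proportion of women assigned to LTW will attend treatment following a referral, compared to TAU". That can be read as all women assigned or as women referred.

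The SAP's Data Analysis section plans chi-square tests and relative risks without naming a denominator, and the SAP does not say which aim its outcomes serve.

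**The concern.** One outcome name covers different quantities. The share of an arm that attends treatment measures what assignment to LTW does. The share of referred women who attend measures something else, in a group that the intervention helps to select.

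Protocol 1.0 hypothesises that LTW women will be more likely to screen positive. Protocol 3.0 describes different routes to referral: in LTW a coordinator assesses by phone and books a home telemedicine visit, while TAU uses in-person screening and referral. Screen-positive or referred women in the two arms are therefore not expected to be alike, and randomisation does not protect a comparison between them. The same holds for women who completed a screen.

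Two things are at stake. The primary objective of Aim 1 is to supply effect sizes for the larger trial, so a selected denominator would pass on a non-comparable estimate. For Aim 2, the denominator of the only primary outcome is left open and could be settled after the data are seen.

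**Working it through.** **Inputs.** From the SAP: "Using a chi-square testing framework and a significance level of 0.05 and assuming two-sided hypothesis testing"; groups of 191 (usual care) and 224 (LTWP); example rates, usual care vs LTWP, of screened 65.2% vs 77.7%, positive 21.7% vs 34.2%, referred 12.5% vs 23.1%, attended 2.1% vs 8.3%. From Protocol 2.0, in-person vs LTW: positive 33.33% vs 81.15%, referred 57.63% vs 76.12%, received treatment 16.04% vs 94.91%.

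**Formula.** Power = Φ[(|p2 − p1| − 1.96·SE0)/SE1], where SE0 = √[p̄(1−p̄)(1/n1+1/n2)], SE1 = √[p1(1−p1)/n1 + p2(1−p2)/n2], and p̄ is the pooled proportion.

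**Step 1: reproduce the SAP's 80%.**
- Referred: difference 0.106, SE0 0.0380, SE1 0.0370; Φ(0.85) = 80.3%.
- Attended: difference 0.062, SE0 0.0224, SE1 0.0212; Φ(0.86) = 80.5%.
- Screened and screened positive give 80.6% and 80.8%. The screen-completer set (63 and 221) gives 80.2%, 80.4% and 80.4%.

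The stated figure holds for both SAP sets. Every pair lands on 80–81%, which indicates that the LTWP rates are detectable differences solved for that power, not expected effects.

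**Step 2: which denominator does the SAP's primary set use?** Chain the Protocol 2.0 in-person rates from the SAP's 65.2% screened:
- 0.652 × 0.3333 = 21.7%
- × 0.5763 = 12.5%
- × 0.1604 = 2.0% (SAP: 2.1%)

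The SAP's usual-care rates are step-by-step rates multiplied through to the whole group. They are not the nested proportions of Protocol 4.0.

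**Step 3: apply the nested denominators to the SAP's group sizes.**
- Screen-positive: 191 × 0.217 = 41.4 and 224 × 0.342 = 76.6.
- Referred: 191 × 0.125 = 23.9 and 224 × 0.231 = 51.7.

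| Comparison | Rates assumed | Usual care vs LTW | Power |
|---|---|---|---|
| Referred among positives | SAP ratios: 12.5/21.7, 23.1/34.2 | 57.6% vs 67.5% | (0.0994 − 1.96×0.0925)/0.0936 = −0.88; 19% |
| Attended among referred | SAP ratios: 2.1/12.5, 8.3/23.1 | 16.8% vs 35.9% | (0.1913 − 1.96×0.1133)/0.1015 = −0.30; 38% (41% by exact enumeration) |
| Referred among positives | Protocol 2.0, read as nested | 57.63% vs 76.12% | 55% |
| Attended among referred | Protocol 2.0, read as nested | 16.04% vs 94.91% | over 99% |

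With these subset sizes, 80% power would need about 57.6% vs 81.8% for referral and 16.8% vs 49.2% for attendance.

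**Step 4: can the definitions disagree?** These scenarios are assumed, for illustration. Let referral rise from 12.5% to 23.1%.
- *Attendance per referral stays at 16.8%.* Whole-group attendance goes from 2.1% to 0.231 × 0.168 = 3.9% (RR 1.85). The nested RR is 1.0.
- *The extra referred women attend at half that rate.* Whole-group attendance is 0.125 × 0.168 + 0.106 × 0.084 = 3.0% (RR 1.42). The nested figure is 3.0/23.1 = 12.9% vs 16.8% (RR 0.77).

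**Step 5: pilot size.** With 100 women at 2:1 (about 33 and 67) and the SAP's example rates, the nested comparisons rest on about 7 vs 23 positives and 4 vs 15 referred women, with power about 8% each. The whole-arm versions have about 22% and 18% by the same approximation, which is rough at such counts. Power is low on either definition.

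**The case against.** The strongest reply is that no power is claimed for the nested endpoints. They belong to a 100-woman pilot meant to estimate effect sizes, while the SAP's 80% concerns 415 women. That stands. A reader might infer that the protocol's version has 19–40% power where 80% was promised. The documents do not support this as a flat statement. The figure comes from dividing detectable differences and placing a pilot endpoint on the SAP's larger groups. The historical rates, read as nested, give 55% and over 99% with the same subset sizes, although they come from an uncontrolled comparison. Low power in a pilot is also no fault in itself.

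A reader might also infer that the Aim 2 primary outcome contradicts the SAP. It does not: it names no denominator, which is a gap. Likewise, the feasibility outcome on attendance is listed separately and need not be the same endpoint.

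Nor do the documents show that the definitions will give opposite answers. Step 4 is hypothetical, its whole-group differences would usually miss significance at 191 and 224 (power about 18% and 8%), and the historical data show higher attendance with LTW.

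Finally, nested proportions are useful for seeing where women drop out of care. That is a reason to report them, not to treat them as a test of efficacy. The selection problem does not depend on power or sample size.

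**Conclusion.** The plan is wrong as written on this point and should be fixed. Referral and attendance sit on at least three denominators across the two documents, and the Aim 2 primary outcome has none. The nested comparisons in Protocol 4.0 and the SAP's screen-completer comparisons condition on events after randomisation that LTW is expected to change, so neither estimates the effect of assignment to LTW.

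The 80% power is correct for the SAP's whole-group and screen-completer sets and does not transfer to the nested ones. Power there runs from about 19% to 55% for referral and from about 38% to over 99% for attendance, depending on whether the SAP's example rates or the historical rates are assumed. These figures use the SAP's group sizes, not the pilot's.

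Two inferences remain. Reading 191 and 224 as whole arms rests on the chained usual-care rates; the SAP never says all randomised women, and its total of 415 does not match the 450 in Protocol 6.0. Reading the Protocol 2.0 rates as nested rests on the same multiplication.

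**What to change.** 1. In Protocol 4.0 (Completion of SBIRT and the Aim 2 primary outcome) and in the SAP's Data Analysis section, name one denominator for each outcome and aim.
2. For the primary between-arm comparisons of screened, screened positive, referred and attended, use all women assigned to the arm. State that this means all randomised women, with a woman who was not screened or not referred counted as not having the later event.
3. Reconcile the SAP's 415 with the protocol's 450, and say which aim or aims the SAP covers.
4. Keep the nested proportions and the screen-completer set as descriptive or supportive results, labelled as non-randomised and not used for efficacy claims or as the effect sizes handed to Aim 2.

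The cost is wording in two documents, with no new data. The downside is that the nested and screened-only percentages lose confirmatory status.

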**Secondary pilot feasibility and acceptability outcome variables include:**

Recruitment: We will determine the proportion of patients who agree to participate as compared to the total number solicited to enroll for each recruitment approach.

Attrition: We will examine the proportion of study participants that prematurely terminate i.e., do not complete screenings, or are unable to be contacted for referral and/or treatment.

Study retention: We will determine the proportion of study participants that complete all assessment points associated with the protocol.

Treatment Attendance: We will collect data from the EHR to determine the proportion of participants that attended a mental health or substance use treatment appointment.

Improved Health-Related Social Needs: Among women referred for treatment, we will compare the change in health-related social needs measured by the Accountable Health Communities (AHC) Health-Related Social Needs (HRSN) Screening Tool among those assigned to LTW, compared to TAU.

Voice Biomarkers: Voice analysis will be completed using an online platform SurveyLex (owned by NeuroLex, Inc.). Among women referred for treatment, we will analyze voice recordings for characteristics (acoustic, linguistic, or meta feature) which may be compared between those assigned to LTW and those assigned to TAU, and compared to other measures collected in either LTW or TAU including EPDS, NIDA Modified Assist, and/or AHC HRSN.

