To address these barriers we designed, implemented and piloted LTW in routine perinatal care in one obstetric practice (see 3.0 Intervention to be Studied) as part of a quality improvement project. Our pilot demonstrates high rates of participation with 87.78% (273/311) of women approached agreeing to take part in LTW and completing the text-message screening. Preliminary data comparing LTW (N=273) to a historical dataset extracted from the EHR including peripartum women receiving in-person SBIRT in the same clinic (N=2,988) found a significantly greater proportion of women enrolled in LTW screened positive (81.15% vs. 33.33%;  $\chi^2=169.50$ ,  $p<0.0001$ ), were referred for treatment (76.12% vs. 57.63%;  $\chi^2=18.03$ ,  $p<0.0001$ ), and received treatment (94.91% vs. 16.04%;  $\chi^2=245.41$ ,  $p<0.0001$ ), compared to women receiving in-person SBIRT.

While these preliminary data are exciting, a randomized control trial will be necessary to determine the feasibility and efficacy of LTW. The goal of Specific Aim 1 is to examine the feasibility and preliminary efficacy of the proposed RCT methodology. Specific Aim 1 will inform Specific Aim 2 to then conduct a larger-scale RCT that examines LTW, compared to a control condition. This will allow us to identify and address barriers in recruitment, retention, use of LTW, and other procedures essential to successful conduct of the RCT. This approach is consistent with expert recommendations to use pilot mechanisms to test the feasibility of doing a full-scale RCT, use data yielded by the pilot study to “de-bug” the methodology, and to assess optimal strategies to executing the RCT [51- R34].

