## **10.0 Study Design / Methods**

Specific aim 1: A two arm pilot RCT (N=100) with 2:1 allocation will examine feasibility and preliminary efficacy of LTW, compared to TAU. Specific aim 2: A RCT (N=350) with 2:1 allocation will examine effectiveness of LTW, compared to TAU. As of the approval of amendment #12 the allocation will switch to 1(LTW):2(TAU) for specific aim 2. Recruitment will primarily occur proactively and remotely via the EHR. We will conduct a weekly EHR search via a recruitment report for all new pregnant and postpartum patients in the past week. The report will include mrn, age, race, ethnicity, date of prenatal care visit, date of postpartum visit, delivery date, ob/gyn provider name, MyChart account (Yes/No), cell phone number, email address and current ICD-9 or 10 diagnoses. Any patients who have not opted out of being contacted for research will be contacted and invited to participate. The study team will not cold-contact any patients who have chosen to opt-out of receiving contact about research or who have met the maximum number of contact attempts at the time of recruitment. If the potential participant has not opted out of being contacted, or the potential participant's provider has agreed to have the study team contact their patient, a phone call will be made or message will be sent via text, email or MyChart message to the potential participant inviting them to take part in the study. This invitation will include clear opt out procedures should the patient not wish to be contacted in the future for the purpose of this study. If interested, participants will complete a screening online via REDCap to determine study eligibility (see above for inclusion criteria). After completing preliminary determination of eligibility, if eligible and interested in participating in the study, participants will be scheduled for a time to complete informed consent (see 9.0 Consent Process).

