Following consent, all participants will subsequently be text messaged and/or emailed a REDCap link, accessible via smartphone, tablet, or computer to complete study assessments. Assessments that need to be completed by interview will be scheduled with study staff and completed via doxy.me or telephone. For specific aim 1 participants only, participants will also complete voice analysis through Surveylex. Participants will be presented with a questionnaire consisting of one task to complete through the Surveylex online form. One task to be answered and entered as text, and three tasks involving voice recordings in response to prompts. The tasks in the online form include the following: Text question (one task): 1) What is your participant ID?; Voice recording (three tasks): During voice recording tasks, the participant will be reminded that there is no right or

wrong answer for these tasks and that they may choose to skip the question or stop their answer at any time 1) Please repeat this phrase: "The quick brown fox jumped over the lazy dogs." (10 seconds) 2) Please describe yesterday from start to finish (30 seconds) and 3) Please describe what brings you happiness (30 seconds). Assessments will occur at baseline (following consent). Participants will be randomized to LTW or TAU, respectively.

Survey assessments are estimated to take 30 minutes to complete and will be administered remotely via REDCap through our established procedures and via doxy.me or telephone for interview assessments. Voice analysis for specific aim 1 participants only takes less than 10 minutes to complete and can be completed remotely. Participants will be compensated via electronic gift cards which will be emailed or texted to participants. Participants will receive \$25 for completion of the baseline assessments. To encourage participants to complete all 3 surveys, participants will be paid an additional \$20 if they complete all 3 surveys (baseline).

Assessments include

Measures	Baseline
Consent	X
Randomization	X
Demographics Questionnaire	X
EPDS Survey	X
NIDA Modified Assist	X
Accountable Health Communities (AHC) Health-Related Social Needs (HRSN) Screening Tool	X
The Medical Outcomes Study Short Form Survey 36 (SF-36v2)	X
*Voice Biomarkers	X
**GAD-7 Anxiety	X
***Columbia Suicide Severity Rating Scale (CSSRS)	X
***Timeline Follow-Back (TLFB)	X
***Usability Scale Survey	X

\*Only the 100 participants in specific aim 1 complete voice biomarkers

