#### **Protections Against Loss of Confidentiality**

All screening information will be kept in a password protected REDCap database. Only key study personnel will have access to the database. If an individual is not eligible to participate based on her answers to the eligibility survey, her screener will not include her name or contact information. Only people who meet eligibility criteria based on the answers to the eligibility survey will be asked if they would like to be contacted about participation in the study and for their name and contact information. Eligible participants' full name, telephone number and

e-mail address will be recorded in the study enrollment log located on a secure MUSC drive or in MUSC Box. The REDCap database and the study enrollment log are the only places where participants' names and subject identification numbers appear together. Eligible participants will be assigned a subject number, will complete informed consent, will be randomized, will complete baseline assessments, and subsequently will receive their randomized intervention.

Upon completing eligibility screening, if study eligible, individuals will be provided with an overview of the study, asked to review study procedures via a consent form, and asked to provide signed consent. Participants will be informed of limitations of confidentiality (i.e., abuse or neglect, intention to harm self or someone else) both verbally and/or in writing during the informed consent process. The consent form will include the participant's name, but not his/her subject number. Consent forms will be provided in English.

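### Aim 1 voice recordings are made once, at baseline, yet are analysed only in women later referred; the optional arm contrast cannot show an LTW response, and the restriction leaves usable recordings out

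*Protocol*

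**What the plan says.** Protocol section 4.0, under the secondary pilot outcomes of Specific Aim 1, defines the voice analysis set: "Among women referred for treatment, we will analyze voice recordings for characteristics (acoustic, linguistic, or meta feature". It names two uses. The first is an arm contrast, worded permissively: features "which may be compared between those assigned to LTW and those assigned to TAU". The second is an association: features "compared to other measures collected in either LTW or TAU including EPDS, NIDA Modified Assist, and/or AHC HRSN".

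Protocol section 10.0 sets who records and when. The table footnote reads "Only the 100 participants in specific aim 1 complete voice biomarkers". The text says "Assessments will occur at baseline (following consent", and the assessment table has a single Baseline column with no later visit.

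Protocol section 13.0, under Protections Against Loss of Confidentiality, gives the order of events: eligible participants "will be randomized, will complete baseline assessments, and subsequently will receive their randomized intervention".

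The SAP contains no voice analysis. It describes every study outcome as dichotomous.

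**The concern.** Three features of the plan do not fit together.

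1. **Timing.** A single recording made before LTW is delivered carries no information about a response to LTW. A larger sample would not change that.
2. **Analysis set.** Referral follows randomisation, and it is one of the steps LTW is meant to change; section 4.0 makes it part of a primary pilot outcome. Keeping only referred women undoes the balance that randomisation gave. Women referred under LTW and under TAU may differ at baseline because the two routes select differently.
3. **Lost data.** Relating voice to questionnaire scores at baseline is a sound cross-sectional question, and nothing in it depends on referral. Limiting it to referred women costs sample size for no gain.

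At stake are an authorised contrast with no causal reading and an imprecise estimate of the one association that the data can support.

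**Working it through.** **Inputs**
- Aim 1 size and ratio (Protocol 10.0): "A two arm pilot RCT (N=100) with 2:1 allocation". I take this as 67 LTW and 33 TAU, because the later Aim 2 switch is written as 1(LTW):2(TAU).
- Quality-improvement pilot (Protocol 2.0): screened positive 81.15% LTW, 33.33% in-person; referred 76.12% and 57.63%. I read the referral figures as shares of those screening positive, because 57.63% exceeds the 33.33% positive rate.
- SAP, referred: 23.1% LTW and 12.5% usual care among all participants; 15.3% and 3.2% among those screened. SAP, screened: 77.7% and 65.2%.
- Two-sided 0.05 and 80% power (SAP), so 1.960 + 0.842 = 2.802.

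**Reproducing the SAP's referral figure.** No power is stated for voice. The nearest stated figure is 80% for 12.5% versus 23.1% with 191 and 224 women.
- Pooled proportion = (191×0.125 + 224×0.231)/415 = 0.182.
- Null SE = √[0.182×0.818×(1/191 + 1/224)] = 0.0380.
- Alternative SE = √[0.125×0.875/191 + 0.231×0.769/224] = 0.0370.
- Power = Φ[(0.106 − 1.960×0.0380)/0.0370] = Φ(0.85) = 0.80.

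The same formula gives 0.804 for 3.2% versus 15.3% with 63 and 221. Both agree with the SAP.

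**Expected referred women.** Count = 67×p(LTW) + 33×p(TAU).

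| Rates used | p(LTW) | p(TAU) | LTW + TAU | Unanalysed of 100 |
|---|---|---|---|---|
| Pilot, everyone screened (0.8115×0.7612; 0.3333×0.5763) | 0.618 | 0.192 | 41.4 + 6.3 = 47.7 | 52% |
| Pilot × SAP screening rates | 0.480 | 0.125 | 32.2 + 4.1 = 36.3 | 64% |
| SAP, all participants | 0.231 | 0.125 | 15.5 + 4.1 = 19.6 | 80% |
| SAP, among screened | 0.153 | 0.032 | 10.3 + 1.1 = 11.3 | 89% |

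Totals are from unrounded counts. If only the LTW pilot referral rate were read as a share of all women, the count would be 51.0 + 6.3 = 57.3, leaving 43% unanalysed. I set that aside because it gives the two halves of one comparison different denominators.

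**Detectable arm difference** = 2.802×√(1/n_LTW + 1/n_TAU), from unrounded counts: about 1.2 SD at pilot rates, 1.6 SD at SAP all-participant rates and 2.9 SD at SAP among-screened rates. The last is nominal only, with about one TAU woman. With all 67 and 33 it is 0.60 SD, but that would still be a baseline difference and not an LTW effect.

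**Size of a pure selection difference (illustration).** Assume that voice correlates ρ with severity, and that referral takes the most severe proportion p in each arm. Mean severity among the referred is φ(z_p)/p, where z_p cuts off the upper p. The arm difference in voice is ρ×[φ(z_L)/p_L − φ(z_T)/p_T].
- Pilot rates: ρ×(0.617 − 1.422), which is −0.24 SD at ρ = 0.3 and −0.40 SD at ρ = 0.5.
- SAP all-participant rates: −0.10 to −0.16 SD.
- SAP among-screened rates: −0.21 to −0.35 SD.

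So differential referral alone gives about 0.1 to 0.4 SD with no LTW effect. The figures halve if referral correlates only 0.5 with severity.

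**Precision of the association.** For an assumed r = 0.40, atanh(0.40) = 0.424 and the 95% interval is tanh(0.424 ± 1.96/√(n − 3)):
- n = 20: −0.05 to 0.72
- n = 48: 0.13 to 0.61
- n = 100: 0.22 to 0.55

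These hold r fixed, so they show the loss from sample size only.

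**The case against.** The best reply is that little rides on this. The arm contrast is optional, sits among secondary pilot outcomes, has no hypothesis attached, and has no counterpart in the SAP. That stands and limits the impact. It does not rescue the analysis set: the limit to referred women is not optional, and a contrast with no interpretation should not be authorised.

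The size is also open to challenge. The SAP's LTW rates are examples of detectable differences, not forecasts for Aim 1. At the pilot rates the unanalysed share is only just over half. Protocol 8.0 uses diagnosis codes to help reach enough women likely to screen positive, which could push referral higher. All of that stands.

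The schedule itself is not clean. Section 10.0 pays for completing three surveys yet labels them baseline; section 4.0 has change outcomes and a retention measure over all assessment points; and the Baseline column holds a usability scale for LTW participants, which presupposes some use of LTW. Later recordings may once have been planned, but the current text schedules none. Even with them, a contrast in referred women would keep the selection problem.

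A reader might go further in three ways that the documents do not support:
- **That the trial will report an LTW voice effect.** No passage claims or plans one.
- **That restricting to referred women must narrow the score range and weaken correlations.** This is plausible but not shown. Referral follows the SBIRT screen, which spans several problems, and a coordinator's assessment; no score distributions are given.
- **That voice and questionnaire data are paired on the same day in all 100 women.** Section 10.0 uses separate online forms, promises no common day, and lets women skip voice tasks.

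**Conclusion.** The point holds for the plan as currently written. The recording is a single pre-intervention measurement, so an LTW-versus-TAU voice contrast among referred women can reflect only chance or differential referral. This rests on the Baseline-only table and the stated order of events, not on any assumed number.

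The cost in data is an estimate: 52% to 89% of recordings unanalysed, with about 1 to 6 TAU women included. It assumes a 67:33 split, a usable recording from every woman, and the documents' referral rates applying to Aim 1. A reader might infer that most recordings are certain to be thrown away. The documents support neither half: the share is inferred and only narrowly exceeds half at the pilot rates, and the recordings are stored (Protocol 11.0), so they are unanalysed, not lost.

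The consequence is confined to one exploratory secondary pilot outcome. It touches no primary outcome, power statement or Aim 2 conclusion. The change is worth making because it costs almost nothing.

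**What to change.** In Protocol 4.0, Voice Biomarkers under Specific Aim 1, delete the opening restriction to referred women and the LTW-versus-TAU comparison. Replace them with a sentence to this effect: in all Aim 1 participants with a usable baseline recording, both arms pooled, voice features will be related to baseline EPDS (9-item), NIDA-Modified ASSIST and AHC HRSN scores as an exploratory analysis.

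Do not describe the measures as same-day. Do not add a model predicting referral from voice within arm; about 1 to 6 referred TAU women could not support one.

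Reconcile the section 4.0 endpoint text with the Baseline-only schedule in section 10.0, including the payment sentence about three surveys. If later recordings exist, say so; any arm comparison of them should use all randomised Aim 1 women, not those referred.

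Cost: the protocol wording above and one line of analysis text, since the SAP has none for voice. No new data are needed. The sponsor gives up an optional contrast that could not be interpreted.
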